1.7 SUMMARY OF CLINICAL DATA FOR GDC-0032

1.7.1 Clinical Safety Data with GDC-0032

As of 5 July 2013, a total of 144 patients have been treated with GDC-0032 capsules, in the Phase I/II PMT4979g study, either as single agent (n=90, 63%) or in combination with endocrine therapy (n=54, 37%).

As of 5 July 2013, enrollment into the dose-escalation stage of Study PMT4979g had been completed with 34 patients enrolled at GDC-0032 doses ranging from 3–16 mg daily. GDC-0032 was well tolerated in the first three cohorts (3, 5, and 8 mg), with no patients experiencing a dose-limiting toxicity (DLT). At the 16-mg dose level, 2 of the 11 safety-evaluable patients experienced a DLT (Grade 4 hyperglycemia and Grade 3 fatigue). At the 12-mg dose level, 1 of the 10 safety-evaluable patients experienced a DLT of Grade 3 acute renal failure. Although the single-agent GDC-0032 maximum tolerated dose (MTD) was not exceeded at the 16-mg dose level, the recommended GDC-0032 dose and schedule for the single-agent expansion cohorts is 9 mg daily on the basis of long-term safety data through multiple treatment cycles. As of the cutoff date, a total of 53 patients had been enrolled in the 9-mg daily dosing expansion cohorts.

As of 5 July 2013, adverse events of any grade that occurred in $\geq 10\%$ of the 87 patients treated with daily single-agent GDC-0032 capsules and were investigator-assessed as related to GDC-0032 were as follows: diarrhea (47%), hyperglycemia (38%), nausea (36%), fatigue (35%), decreased appetite (31%), rash (25%), stomatitis (13%), vomiting (13%), and mucosal inflammation (12%). Grade 3 and 4 adverse events assessed by the investigator as GDC-0032 related included hyperglycemia (12%), colitis (6%), rash (5%), diarrhea (3%), fatigue (3%), pneumonitis (3%), pruritus (2%), stomatitis (2%), increased alanine aminotransferase levels (1%), anemia (1%), increase in blood creatinine (1%), exfoliative rash (1%), hypokalemia (1%), hypophosphatemia (1%), lung infection (1%), pneumonia (1%), erythematous rash (1%), generalized rash (1%), maculopapular rash (1%) and skin exfoliation (1%), and acute renal failure (1%).

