As of 5 July 2013, a total of 27 patients have been enrolled in the expansion cohort of GDC-0032 at dose levels of 6 and 9 mg daily (19 patients at 6 mg, and 8 patients at 9 mg) daily in combination with letrozole (Cohort E). No DLTs were observed at either dose level. Adverse events of any grade and assessed by the investigator as drug related that occurred in $\geq 10\%$ of the 27 safety-evaluable patients assessed as related to GDC-0032 were diarrhea (67%), fatigue (30%), nausea (30%), rash (30%), decreased appetite (26%), hyperglycemia (26%), stomatitis (26%), dysgeusia (22%), mucosal inflammation (19%), asthenia (15%), pruritis (15%), vomiting (15%), and dry mouth (11%). Grade 3 and 4 adverse events assessed by the investigator as GDC-0032 related include diarrhea (11%), mucosal inflammation (7%), increased amylase (4%), hyperglycemia (4%), increased AST (4%), stomatitis (3.7%), increased blood alkaline phosphate (4%), fatigue (4%), increased gamma-glutamyltransferase in the blood (4%), hypokalemia (4%), increased lipase in the blood, (4%), and papilloedema (4%).

As of 5 July 2013, a total of 27 patients have been enrolled in the expansion cohort of GDC-0032 at dose levels of 6 and 9 mg daily (21 patients at 6 mg and 6 patients at 9 mg) in combination with fulvestrant (Cohort F). No DLTs were observed at either dose level. One patient has been enrolled in the Phase II part of the study with 6 mg GDC-0032 in combination with fulvestrant. Adverse events assessed by the investigator as GDC-0032 related and of any grade that occurred in $\geq 10\%$ of the 27 patients and were assessed as related to GDC-0032 were diarrhea (48%), hyperglycemia (33%), nausea (33%), decreased appetite (26%), fatigue (26%), rash (26%), stomatitis (22%), asthenia (19%), muscle spasms (15%), vomiting (15%), dysgeusia (11%), gastroesophageal reflux disease (11%) and mucosal inflammation (11%). Grade 3 and 4 adverse events assessed by the investigator as related to GDC-0032 included hyperglycemia (15%), diarrhea (7%), dyspnea (4%), flank pain (4%), hyponatremia (4%), neutropenia (4%), rash (4%) and vomiting (4%).

Please refer to the GDC-0032 Investigator's Brochure for additional information.

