5.1.1.1 Management of Hyperglycemia

Metformin is the first antihyperglycemic medication of choice because of the lower risk of hypoglycemia with this agent. Because metformin in some patients may also cause diarrhea and not be well tolerated, other antihyperglycemic medications such as sulfonylureas (e.g., glimepiride, glipizide) can be used. Extra caution should be used with other drugs such as sulfonylureas because of the increased risk for hypoglycemia with these agents. Consultation with an endocrinologist can be helpful in managing hyperglycemia.

Specific dose modification and management guidelines for hyperglycemia are provided in [Table 2](#).

Table 2 Dose Modification and Management Guidelines for Hyperglycemia (Based on Fasting Blood Glucose)

Grade	Dose Modification and Management Guidelines for Hyperglycemia (based on fasting blood glucose)
Grade 2	Initiation of an anti-hyperglycemic agent (e.g., metformin) and additional glucose monitoring will be implemented. Dosing with GDC-0032/ placebo may either be held or continued per investigator evaluation.
Grade 3 (asymptomatic)	GDC-0032/ placebo dosing will be suspended and the patient will be managed as per standard of care, including implementation of additional glucose monitoring and initiation of, or an increase in, the dose of an anti-hyperglycemic therapy (e.g., metformin). If the hyperglycemic event does not improve to Grade ≤ 1 within 28 days, GDC-0032/ placebo will be permanently discontinued. If the hyperglycemic event improves to Grade ≤ 1 within 28 days, GDC-0032/ placebo dosing may resume at one dose level lower, with approval by the Medical Monitor.

Grade	Dose Modification and Management Guidelines for Hyperglycemia (based on fasting blood glucose)
Grade 3 (symptomatic) ^a , Grade 3 (requiring hospitalization), or Grade 4	GDC-0032/ placebo dosing will be suspended, and the patient will be managed as per standard of care, including implementation of additional glucose monitoring and initiation of, or an increase in, the dose of anti-hyperglycemic therapy. If the hyperglycemic event does not improve to Grade ≤ 1 within 28 days, GDC-0032/ placebo will be permanently discontinued. If the hyperglycemic event improves to Grade ≤ 1 within 28 days, GDC-0032/ placebo dosing may resume at one dose level lower, with approval by the Medical Monitor.

^a For example, blurred vision, frequent urination, excessive thirst.

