Appendix 1 Schedule of Assessments (cont.)

Study procedures	Screening	Treatment Phase								Surgery ^{a,f}	Post-Surgery
		W1	W3	W5	W7	W9	W11	W13	W16 (Presurgical Visit)	W17–W18 (Surgery)	4 Weeks (±1W) from Surgery
Days	-28 to -1	1	15 (+2)	29 (±2)	43 (±2)	57 (±2)	71 (±2)	85 (±2)	106–112	113–126	
Fasting serum chemistry ^j	x	x		x		x		x	x		x
Glycosylated hemoglobin (Hb _{A1c})	x										
Fasting insulin and glucose ^k	x	x		x		x		x	x		x
Fasting lipid profile and amylase ^l	x			x				x	x		x
Coagulation (INR and aPTT)	x			x		x		x	x		x
Urinalysis (laboratory) ^m	x			x		x			x		x
DL _{CO} ⁿ	x								x		
Bone mineral density test ^o	x										
Blood sample for plasma protein biomarkers ^p		x				x			x		x
Blood sample for ctDNA ^q		x				x			x		x
Blood sample for NGS ^r		x									
Pharmacogenomic sample ^s		x									
Concomitant medication ^t	x	x	x	x		x		x	x		x
Adverse events	x	x	x	x	x	x	x	x	x		x
Inclusion/exclusion criteria ^u	x										
Visit with breast surgeon (may occur from Week 13)								x			
Surgery ^v										x	

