Appendix 1 Schedule of Assessments (cont.)

-
- ^f Baseline evaluation of axillary lymph nodes assessed with ultrasound.
- ^g MRI evaluation is optional at Week 9. MRI is mandatory at Week 9 in the event that disease progression is suspected, or if the primary lesion is not evaluable by ultrasound at baseline. Send all scans to the central reading facility for evaluation.
- ^h Two formalin-fixed, paraffin-embedded core needle biopsies and one freshly frozen OCT core needle biopsy are required prior to initiation of treatment (pretreatment) and also on Day 15. A formalin-fixed, paraffin-embedded tumor block from a surgical resection is required at surgery (Weeks 17–18). *Except in the case of pCR, every effort should be made to obtain a fresh-frozen tumor tissue sample at surgery.*
- ⁱ Complete blood count includes red blood cell count, hemoglobin, hematocrit, white blood cell count with differential (neutrophils, bands, eosinophils, basophils, lymphocytes, monocytes, and other cells, *if applicable*), and platelet count. Screening results may be valid for Week 1, Day 1 if performed within 7 days prior to Week 1, Day 1.
- ^j Fasting (≥ 10 -hour fast) serum chemistry: BUN, creatinine, sodium, potassium, magnesium, bicarbonate, calcium, phosphorus, total protein, albumin, serum bilirubin, alkaline phosphatase, glucose, AST, and ALT. Screening results may be valid for Week 1, Day 1 if performed within 7 days prior to Week 1, Day 1.
- ^k Screening results may be valid for Week 1, Day 1 if performed within 7 days prior to Week 1, Day 1.
- ^l Fasting lipid profile includes total cholesterol, HDL, LDL, triglycerides, amylase, and lipase. Screening results may be valid for Week 1, Day 1 if performed within 7 days prior to Week 1, Day 1.
- ^m Includes specific gravity, pH, glucose, protein, ketones, and blood. Screening results may be valid for Week 1, Day 1 if performed within 7 days prior to Week 1, Day 1.
- ⁿ DL_{CO} is obtained at screening and prior to surgery. The DL_{CO} test should be repeated if there is clinical suspicion of pneumonitis. DL_{CO} calculations are described in Appendix 7. The hemoglobin value used for correcting DL_{CO} should represent the patient's actual hemoglobin level and should be obtained within 7 days of the DL_{CO} test.

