Appendix 2 Schedule of Pharmacokinetic Assessments

Visit	Timepoint	PK Assessments
Day 1	3 hours post (± 60 min) letrozole and GDC-0032/placebo administration	Letrozole PK
		GDC-0032 PK
Day 15 (+ 2 days)	0–4 hours prior to letrozole and GDC-0032/placebo administration	Letrozole PK
		GDC-0032 PK
	3 hours (± 60 min) post letrozole and GDC-0032/placebo administration ECG before PK	Letrozole PK
		GDC-0032 PK
Day 57 (+/- 2 days)	3 hours post (± 60 min) letrozole and GDC-0032/placebo administration	Letrozole PK GDC-0032 PK

ECG=electrocardiogram; min=minutes; PK=pharmacokinetics.

Record exact time of dose administration and sample collection.

Appendix 3

Modified Response Evaluation Criteria in Solid Tumors: Assessment of Response of Neoadjuvant Therapy in Early Breast Cancer

Conventional response criteria may not be ideal for the assessment of response in the setting of neoadjuvant therapy in early breast cancer. Therefore, RECIST 1.1 criteria have been modified to specifically address assessment of primary breast lesions along with axillary lymph node disease, using a range of breast imaging modalities. Selected sections from the Response Evaluation Criteria in Solid Tumors (RECIST), Version 1.1¹ are presented below, with modifications and the addition of explanatory text as needed for clarity. For detailed information on the read methodology including how imaging data should be processed prior to reads, please refer to the Study Imaging Charter.

	RECIST v1.1	Modified RECIST Early Breast Cancer Neoadjuvant Therapy
Modalities	CT as primary modality, ultrasound not recommended	No CT; primary assessments by MRI; also assessments by ultrasound, mammography, and clinical exam
Lymph nodes	May be considered target lesions based on size criteria (≥ 15 mm in SAD)	Only axillary lymph nodes assessed; nodes that are considered abnormal on imaging (based on morphological factors including, but not limited to SAD) to be followed as non-target lesions
Possibility of having only non-target disease	Allowed	Not allowed; primary breast lesions must be measurable by MRI

CT=computed tomography; MRI=magnetic resonance imaging; SAD=short axis dimension.

BASELINE DOCUMENTATION OF TARGET AND NON-TARGET LESIONS

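### Appendix 1 schedules no glucose between the predose Day 1 value and Day 29, so no scheduled assessment in the first four weeks can trigger Table 2's row for asymptomatic Grade 3 hyperglycemia

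*Protocol*

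**What the plan says.** The action rule is in Section 5.1.1.1. Table 2 is titled "Dose Modification and Management Guidelines for Hyperglycemia (Based on Fasting Blood Glucose" and gives Grade 2, asymptomatic Grade 3, and symptomatic or worse events separate rows. For asymptomatic Grade 3, study drug is suspended. The extra glucose monitoring named in the table begins only once an event of Grade 2 or higher has been found.

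The measurements are set in Appendix 1; Section 4.5.10 leaves their frequency to that schedule. Two blood rows contain glucose: "Fasting insulin and glucose ^k" and "Fasting serum chemistry ^j", whose footnote lists "total protein, albumin, serum bilirubin, alkaline phosphatase, glucose, AST, and ALT". Both are marked at Screening and Weeks 1, 5, 9, 13 and 16 and after surgery. Neither is marked at Week 3.

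The patient nevertheless attends at Week 3 (Day 15, +2) for vital signs, ECG, biopsy, drug accountability and adverse event review. Appendix 2 adds a pharmacokinetic blood sample "0–4 hours prior to letrozole and GDC-0032/placebo administration".

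**The concern.** By definition, an asymptomatic laboratory event does not come to light when a patient is asked how she feels, and Section 5.3.2 asks for non-directive questioning. A rule that suspends dosing for such an event works only as often as glucose is measured. For the first four weeks on study drug nothing is scheduled that could set it off, although the protocol's own Phase I data show hyperglycemia to be a common effect of GDC-0032. At stake is delayed detection: dosing continues until Week 5 in a patient who already meets the Table 2 condition, and an event that comes and goes before Week 5 never enters the laboratory tables by grade planned in Section 6.5.

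**Working it through.** The protocol states no figure to reproduce here. The check is a reading of the schedule followed by a count of days and doses.

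**1. Every possible source of a glucose value (Appendix 1)**

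| Row | Screening | W1 | W3 | W5 | W9 | W13 | W16 | Post-surgery |
|---|---|---|---|---|---|---|---|---|
| Fasting insulin and glucose | x | x | – | x | x | x | x | x |
| Fasting serum chemistry | x | x | – | x | x | x | x | x |
| Urinalysis (includes glucose) | x | – | – | x | x | – | x | x |
| HbA1c | x | – | – | – | – | – | – | – |

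Weeks 7 and 11 carry none of these; those contacts may be by telephone. Sections 4.5.10 and 5.1.1.1 add no routine draw.

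**2. Status of the Day 1 value.** The general note to Appendix 1 places assessments before dosing unless stated otherwise. The footnotes to both glucose rows let a screening result up to 7 days old stand in for Day 1. It is therefore a baseline value.

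**3. Length of the gap**
- Nominal: 29 − 1 = 28 days.
- With the ±2-day window: 27 − 1 = 26 to 31 − 1 = 30 days.
- With a 7-day-old screening value in place of Day 1: at most 30 + 7 = 37 days.

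**4. Doses taken before the first on-treatment glucose**, assuming the 5-on/2-off cycle starts on Day 1
- Planned: 16 weeks × 5 = 80.
- Before a draw on Day 27 or Day 29: 4 × 5 = 20, or 20/80 = 25%.
- Before a draw on Day 31: 20 + 2 = 22, or 22/80 = 27.5%.

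**5. Whether exposure is already present.** Section 1.7.1.1 reports 2- to 4-fold accumulation after 8 days of daily dosing. Five half-lives at about 40 h are 5 × 40/24 = 8.3 days. Under the intermittent schedule the level will differ, but accumulation is well under way by Day 15 and long before Day 29.

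**6. Background frequency (Section 1.7.1; daily capsules, all treatment, investigator-assessed as related)**
- With letrozole: 26% any grade, 4% Grade 3-4.
- Single agent: 38% and 12%.
- With fulvestrant: 33% and 15%.

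Neither the time of onset nor the share without symptoms is given, so these rates cannot be converted into a number falling before Day 29.

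**The case against.** The strongest reply is that the two passages do not conflict. Table 2 says what to do with a graded value and sets no sampling frequency. Appendix 1 sets that frequency, and its later spacing is the same: Week 5 to Week 9 and Week 9 to Week 13 are also 28 days. Unscheduled draws are not forbidden, adverse events are reviewed at Day 15, entry requires fasting glucose of 125 mg/dL or less, and diabetes requiring medication is excluded. All of this stands. It makes the point a monitoring gap rather than a contradiction, and it lowers the risk. It does not close the gap: the first interval is the only one with no earlier on-treatment value behind it, and the safeguards either act before treatment or depend on symptoms or on someone choosing to test.

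A reader might infer more than the documents support:

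- *That incidence and time to onset are generally understated.* Hyperglycemia that persists under continued dosing is found at Week 5; only events that resolve earlier are lost. Time to onset is not listed in Section 3.4.2 or Section 6.5.
- *That the 20-patient iDMC review is compromised.* It follows the post-surgery visit or 20 weeks on study. Patients who complete the schedule have by then had the Week 5, 9, 13 and 16 draws.
- *That the later draws are badly timed because they follow two off-days.* If the cycle starts on Day 1, Days 13 and 14 are also off, so Day 15 has the same position in the week. Nothing in the protocol ties fasting glucose to that morning's drug level.
- *That the Phase I rates multiplied by the roughly 165 patients expected on GDC-0032 give the cases missed.* Those rates cover all treatment under daily dosing, with single-agent doses up to 16 mg. The cohort closest to this trial, with letrozole, has the lowest Grade 3-4 rate.

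**Conclusion.** The point holds as a gap between the assessment schedule and the rule it serves. For 26 to 30 days from Day 1, covering 20 to 22 of 80 planned doses, no scheduled assessment can trigger the asymptomatic Grade 3 row of Table 2. The consequence is late detection of early asymptomatic events, and loss of those that resolve before Week 5. The number of patients affected is unknown, because onset times and the asymptomatic share are not given. The conclusion rests on Appendix 1 being complete as printed, and the dose count on a 5-on/2-off cycle starting on Day 1. The gap is worth closing because the protocol itself documents the risk and the patient is already on site with blood being drawn.

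**What to change.** Reconcile Appendix 1 with Table 2 so that a fasting glucose is available within the first four weeks of treatment. The existing schedule allows this without a new visit: the fasting insulin and glucose row can be marked at Week 3 (Day 15, +2) and the sample taken with the predose pharmacokinetic draw. The sponsor should confirm the timing. The cost is one additional tube from a venipuncture that already takes place, and the patient has to attend that visit fasted. No dose, grading or treatment rule changes.

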Appendix 1 Schedule of Assessments (cont.)

Study procedures	Screening	Treatment Phase								Surgery ^{a,f}	Post-Surgery
		W1	W3	W5	W7	W9	W11	W13	W16 (Presurgical Visit)	W17–W18 (Surgery)	4 Weeks (±1W) from Surgery
Days	-28 to -1	1	15 (+2)	29 (±2)	43 (±2)	57 (±2)	71 (±2)	85 (±2)	106–112	113–126	
Randomization	x										
Letrozole accountability/dispensation		x	x	x		x		x	x		
GDC-0032/placebo accountability/dispensation		x	x	x		x		x	x		
Patient-reported outcomes ^w		x		x		x		x	x		x
Pharmacokinetic sample (see Appendix 2)		x	x			x					

aPTT = activated partial thromboplastin time; CA-125 = cancer antigen 125; CTCs = circulating tumor cells; ctDNA = circulating tumor DNA; DL_{CO} = diffusion capacity of the lung for carbon monoxide; ECG = electrocardiogram; ECOG = Eastern Cooperative Oncology Group; INR = international normalized ratio; MRI = magnetic resonance imaging; NGS = next-generation sequencing.

Note: All assessments should be performed before dosing, unless otherwise stated. Some assessments may be performed outside the window indicated to accommodate holidays, unforeseen scheduling issues, or ongoing safety issues with the trial and the patient, after approval by the Medical Monitor.

- ^a Perform within 28 days prior to Day 1 of Cycle 1. Signed informed consent must be provided prior to any study-specific evaluations. Assessments performed as standard of care within the timeframe may be used.
- ^b Medical history includes clinically significant diseases that are currently active or that were active within the last 5 years, surgeries, cancer history (including date of diagnosis, primary tumor histology, grade, staging, prior cancer therapies, and procedures), reproductive status, smoking history, use of alcohol and drugs of abuse. Demographic data include age, sex, and self-reported race/ethnicity.
- ^c A complete physical examination should include an evaluation of the head, eyes, ears, nose, and throat, and the cardiovascular, dermatological, musculoskeletal, respiratory, gastrointestinal, genitourinary, and neurological systems as well as weight (in kilograms) and height (in centimeters; height is measured at the screening visit only). Perform symptom-directed physical examination after baseline assessment.
- ^d Vital signs include measurements of heart rate, respiratory rate, and systolic and diastolic blood pressure while the patient is in a seated position and temperature. Oxygen saturation is obtained by pulse oximetry after the patient has been in a seated position for ≥ 5 minutes. Obtain vital signs predose.
- ^e Triplicate ECG recordings will be obtained at each specified timepoint. A window of ± 30 minutes is acceptable for all timepoints. Submit all ECGs to the diagnostic facility for central review.

Appendix 1 Schedule of Assessments (cont.)

-
- ^f Baseline evaluation of axillary lymph nodes assessed with ultrasound.
- ^g MRI evaluation is optional at Week 9. MRI is mandatory at Week 9 in the event that disease progression is suspected, or if the primary lesion is not evaluable by ultrasound at baseline. Send all scans to the central reading facility for evaluation.
- ^h Two formalin-fixed, paraffin-embedded core needle biopsies and one freshly frozen OCT core needle biopsy are required prior to initiation of treatment (pretreatment) and also on Day 15. A formalin-fixed, paraffin-embedded tumor block from a surgical resection is required at surgery (Weeks 17–18). *Except in the case of pCR, every effort should be made to obtain a fresh-frozen tumor tissue sample at surgery.*
- ⁱ Complete blood count includes red blood cell count, hemoglobin, hematocrit, white blood cell count with differential (neutrophils, bands, eosinophils, basophils, lymphocytes, monocytes, and other cells, *if applicable*), and platelet count. Screening results may be valid for Week 1, Day 1 if performed within 7 days prior to Week 1, Day 1.
- ^j Fasting (≥ 10 -hour fast) serum chemistry: BUN, creatinine, sodium, potassium, magnesium, bicarbonate, calcium, phosphorus, total protein, albumin, serum bilirubin, alkaline phosphatase, glucose, AST, and ALT. Screening results may be valid for Week 1, Day 1 if performed within 7 days prior to Week 1, Day 1.
- ^k Screening results may be valid for Week 1, Day 1 if performed within 7 days prior to Week 1, Day 1.
- ^l Fasting lipid profile includes total cholesterol, HDL, LDL, triglycerides, amylase, and lipase. Screening results may be valid for Week 1, Day 1 if performed within 7 days prior to Week 1, Day 1.
- ^m Includes specific gravity, pH, glucose, protein, ketones, and blood. Screening results may be valid for Week 1, Day 1 if performed within 7 days prior to Week 1, Day 1.
- ⁿ DL_{CO} is obtained at screening and prior to surgery. The DL_{CO} test should be repeated if there is clinical suspicion of pneumonitis. DL_{CO} calculations are described in Appendix 7. The hemoglobin value used for correcting DL_{CO} should represent the patient's actual hemoglobin level and should be obtained within 7 days of the DL_{CO} test.
- ^o Baseline bone mineral density will be measured via dual-energy X-ray absorptiometry (DXA) and will need to be obtained in women with a history of osteoporosis and/or fractures, or who are at increased risk of osteoporosis. DXA measurement of both the hip and lumbar spine is suggested. When either the hip or lumbar spine is not a valid skeletal site for BMD measurement, then the 33% (one-third) radius should be measured. In some patients, measurement of the hip alone could be sufficient.
- ^p Pretreatment sample for plasma protein biomarkers should be obtained prior to dosing. *This sample will also be collected prior to dosing at Week 9, Week 16, and at the 4-week post-surgical visits.* Refer to laboratory manual for more information.
- ^q Pretreatment sample for ctDNA may be obtained on Day 1 prior to dosing. This sample will also be collected prior to dosing at Week 9 and at Week 16, *and at the 4-week post-surgical visits.* Refer to laboratory manual for more information.
- ^r Blood for NGS will be collected if allowed by local regulatory authorities and may be obtained prior to dosing on Week 1.
- ^s Blood for pharmacogenomics will be collected if allowed by local regulatory authorities and may be obtained prior to dosing on Week 1.
- ^t Record all medications used by the patient within 7 days before screening (including prescription, over-the-counter, herbal remedies, and supplements).
- ^u All of the study's inclusion criteria and none of the exclusion criteria should be met prior to study entry.

